9.5.2.2 Description of Procedures/Assessments Schedule

Please refer to [Table 6](#) and [Table 7](#) for the timings of the procedures and assessments to be performed during the study. Screening assessments will be organized into 4 tiers (see [Table 6](#), [Section 9.1.1.1](#), and [Figure 2](#)).

See [Section 9.5.1](#) for a full description of the procedures and assessments to be performed during this study.

Table 8 presents the number of blood and CSF samples, and the total volume of blood and CSF that will be collected throughout the study. Additional samples may be taken at the discretion of the investigator if the results of any tests fall outside reference ranges or if clinical symptoms necessitate testing to ensure subject safety.

Table 8 Summary of Blood and CSF Sample Volumes

| Assessment | Total number of collection time points | Number of time points x volume per collection (mL whole blood or CSF) | | Total volume (mL whole blood or CSF) |
|--|--|---|---------------------------------|--------------------------------------|
| | | Screening and Baseline Periods | Treatment and Follow-Up Periods | |
| Blood | | | | |
| Chemistry | 12 | 2 x 2 mL | 10 x 2 mL | 24 mL |
| Hematology | 18 | 2 x 5 mL | 16 x 5 mL | 90 mL |
| Lymphocyte subset analyses | 18 | 2 x 4 mL | 16 x 4 mL | 72 mL |
| PBMC | 4 | 1 x 16 mL | 3 x 16 mL | 64 mL |
| IgA, IgM, IgG | 9 | 2 x 2 mL | 7 x 2 mL | 18 mL |
| PT, PTT for INR | 2 | 2 x 3 mL | None | 6 mL |
| Thyroid function tests (thyroid stimulating hormone, free triiodothyronine and free thyroxine) | 1 | 1 x 3 mL | None | 3 mL |
| Viral screen (Hepatitis B and C) | 1 | 1 x 4 mL | None | 4 mL |
| Viral characterization | 1 | 1 x 4 mL | None | 4 mL |
| Vitamin B12 | 1 | 1 x 2 mL | None | 2 mL |
| Serum pregnancy test | 1 | 1 x 2 mL | None | 2 mL |
| Tuberculosis (interferon-gamma release assays) | 1 | 1 x 3 mL | None | 3 mL |
| Sample for immune status | 8 | 1 x 4 mL | 7 x 4 mL | 32 mL |
| PD sample | 9 | 1 x 4 mL | 8 x 4 mL | 36 mL |
| PK analysis | 7 | 1 x 3 mL | 6 x 6 mL | 39 mL |
| Pharmacogenetic sample | 1 | 1 x 3 mL | None | 3 mL |
| All blood samples, total volume whole blood collected | | 80 mL | 322 mL | 402 mL |
| CSF (For subjects who consent to CSF sample collection) (revised per Amendment 02) | | | | |
| PD and PK samples | 3 | 1 x 12 mL | 2 x 12 mL | 36 mL |

CSF = cerebrospinal fluid, Ig = immunoglobulin, INR = International Normalized Ratio, PBMC = peripheral blood mononuclear cell, PD = pharmacodynamics, PK = pharmacokinetic, PT = prothrombin time, PTT = partial thromboplastin time.

9.5.3 Appropriateness of Measurements

All clinical assessments are standard measurements commonly used in studies of AD.

Standard safety assessments incorporated into this protocol include vital signs, clinical laboratory assessments, physical examinations, ECG measurements, and reports of AEs. MRI will be used to detect vasogenic edema, macrohemorrhage, an area of superficial siderosis, or a symptomatic microhemorrhage and is a standard evaluation to ensure subject safety. The C-SSRS has been endorsed by the FDA as a measure of potential suicidality ([Guidance for Industry Suicidality](#)).

A number of safety aspects have been built into the design of this study in light of the preclinical and clinical safety data with E2609, in addition to mitigating clinical risk in the progression from 14 days of dosing in the MAD study to 18 months of treatment in this Phase 2 study. Details are provided in [Section 9.2.6](#).

9.5.4 Reporting of Serious Adverse Events, Pregnancy, and Events Associated with Special Situations

9.5.4.1 Reporting of Serious Adverse Events

All SAEs, regardless of their relationship to study treatment, must be reported on a completed SAE form by email or fax as soon as possible but no later than 24 hours from when the investigator becomes aware of the event.

SAEs, regardless of causality assessment, must be collected up to 3 months after the last dose of study drug, ie, through to the second follow-up visit (Visit 20). In subjects who discontinue study drug early, but continue with efficacy assessments, SAEs only need to be solicited up to 3 months after the last dose of study drug. However, any SAEs volunteered by subjects after this time point must be reported according to standard procedures. All SAEs must be followed to resolution or, if resolution is unlikely, to stabilization. Any SAE judged by the investigator to be related to the study treatment or any protocol-required procedure should be reported to the sponsor regardless of the length of time that has passed since study completion.

The detailed contact information for reporting of SAEs is provided in the Investigator Study File.

For urgent safety issues, please ensure all appropriate medical care is administered to the subject and contact the appropriate study team member listed in the Investigator Study File.

It is very important that the SAE report form be filled out as completely as possible at the time of the initial report. This includes the investigator's assessment of causality.

Any follow-up information received on SAEs should be forwarded within 1 business day of its receipt. If the follow-up information changes the investigator's assessment of causality, this should also be noted on the follow-up SAE form.

Preliminary SAE reports should be followed as soon as possible by detailed descriptions including copies of hospital case reports, autopsy reports, and other documents requested by the sponsor.

The investigator must notify his/her IRB/IEC of the occurrence of the SAE in writing, if required by their institution. A copy of this communication must be forwarded to the sponsor, or its designee, to be filed in the sponsor's Trial Master File.

9.5.4.2 Reporting of Pregnancy and Exposure to Study Drug Through Breastfeeding

Any pregnancy in which the estimated date of conception is either before the last visit or within 28 days of last study treatment, or any exposure to study drug through breastfeeding during study treatment or within 28 days of last study treatment, must be reported.

If an adverse outcome of a pregnancy is suspected to be related to study drug exposure, this should be reported regardless of the length of time that has passed since the exposure to study treatment.

A congenital anomaly, death during perinatal period, an induced abortion, or a spontaneous abortion are considered to be an SAE and should be reported in the same time frame and in the same format as all other SAEs (see Reporting of Serious Adverse Events [[Section 9.5.4.1](#)]).

Pregnancies or exposure to study drug through breastfeeding must be reported by fax or email as soon as possible but no later than 1 business day from the date the investigator becomes aware of the pregnancy. The contact information for the reporting of pregnancies and exposure to study drug through breastfeeding is provided in the Investigator Study File. The Pregnancy Report Form must be used for reporting. All pregnancies must be followed to outcome. The outcome of the pregnancy must be reported as soon as possible but no later than 1 business day from the date the investigator becomes aware of the outcome.

A subject who becomes pregnant must discontinue study treatment.

9.5.4.3 Reporting of Events Associated with Special Situations

9.5.4.3.1 REPORTING OF ADVERSE EVENTS ASSOCIATED WITH STUDY DRUG OVERDOSE, MISUSE, ABUSE, OR MEDICATION ERROR

Adverse events associated with study drug overdose, misuse, abuse, and medication error refer to AEs associated with uses of the study drug outside of that specified by the protocol. Overdose, misuse, abuse, and medication error are defined as follows:

| | |
|------------------|--|
| Overdose | Accidental or intentional use of the study drug in an amount higher than the protocol-defined dose |
| Misuse | Intentional and inappropriate use of study drug not in accordance with the protocol |
| Abuse | Sporadic or persistent intentional excessive use of study drug accompanied by harmful physical or psychological effects |
| Medication error | Any unintentional event that causes or leads to inappropriate study drug use or subject harm while the study drug is in the control of site personnel or the subject |

All AEs associated with overdose, misuse, abuse, or medication error should be captured on the Adverse Event eCRF and also reported using the procedures detailed in Reporting of Serious Adverse Events ([Section 9.5.4.1](#)) even if the AEs do not meet serious criteria. Abuse is always to be captured as an AE. If the AE associated with an overdose, misuse, abuse, or medication error does not meet serious criteria, it must still be reported using the SAE form and in an expedited manner but should be noted as nonserious on the SAE form and the Adverse Event eCRF.

9.5.4.3.2 REPORTING OF STUDY-SPECIFIC EVENTS

Study-specific events (as detailed in [Section 9.5.1.5.2](#)) should always be considered serious important medical events and be entered on the Adverse Event eCRF and reported using the procedures detailed in Reporting of Serious Adverse Events ([Section 9.5.4.1](#)), even if the study-specific event does not meet other serious criteria.

9.5.4.4 Expedited Reporting

The sponsor must inform investigators (or as regionally required, the head of the medical institution) and regulatory authorities of reportable events, in compliance with applicable regulatory requirements, on an expedited basis (ie, within specific time frames). For this reason, it is imperative that sites provide complete SAE information in the manner described above.

9.5.4.5 Breaking the Blind

In the case of a medical emergency where the appropriate treatment of the subject requires knowledge of the study treatment given, the investigator may break the randomization code for an individual subject. In all such cases, the AE necessitating the emergency blind break will be handled as an SAE in accordance with the procedures indicated above. Any broken code will be clearly justified and documented. The medical monitor must be notified immediately of the blind break.

9.5.4.6 Regulatory Reporting of Adverse Events

Adverse events will be reported by the sponsor or a third party acting on behalf of the sponsor to regulatory authorities in compliance with local and regional law and established guidance. The format of these reports will be dictated by the local and regional requirements.

All studies that are conducted within any European country will comply with European GCP Directive 2005/28/EC and Clinical Trial Directive 2001/20/EC. All SUSARs will be reported, as required, to the competent authorities of all involved European member states.

9.5.5 Completion/Discontinuation of Subjects

A subject may elect to discontinue study drug or withdraw from the study at any time for any reason. All subjects who discontinue taking study drug prematurely for any reason will undergo an ED Visit within 7 days of their last dose of study drug (see [Section 9.1.2.2](#)). In addition, Follow-Up Visits will be scheduled 4 and 12 weeks after the last dose of study drug (Visit 19 and Visit 20, respectively) (see [Section 9.1.2.3](#)). See [Table 7](#) for full details of the assessments to be performed at these visits. Subjects who discontinue study drug prematurely will also be scheduled to return to the study site for each scheduled visit when clinical efficacy assessments are to be conducted (ie, at Visits 11, 14, 15, 16, 17, and 18, if these visits have not already been performed). At these visits, only clinical efficacy assessments (MMSE, CDR, ADAS-cog14, FAQ, CBB and ISLT) will be conducted. Subjects who discontinue early from study drug are considered on study as long as they return for their regularly scheduled clinical efficacy visits as outlined above. Subjects who discontinue study drug early (as opposed to subjects whose dosing with study drug is temporarily suspended under Medical Monitor guidance) will not be permitted to restart study drug.

The investigator will promptly explain to the subject involved that the study will be discontinued for that subject and will provide appropriate medical treatment and other necessary measures for the subject. A subject who has ceased to return for visits will be followed up by mail, phone, or other means to gather information such as the reason for failure to return, the status of treatment compliance, the presence or absence of AEs, and clinical courses of signs and symptoms.

Subjects who withdraw prematurely from the study will be withdrawn for 1 of these primary reasons: AE(s), lost to follow-up, subject choice, inadequate therapeutic effect, withdrawal of consent, pregnancy, study terminated by sponsor, or other. In addition to the primary reason, the subject may indicate 1 or more secondary reason(s) for withdrawal from the study. Study disposition information will be collected on the Subject Disposition eCRF.

A subject removed from the study for any reason may not be replaced.

9.5.6 Abuse or Diversion of Study Drug

Adverse events associated with abuse or diversion will be appropriately reported as AEs and monitored per [Section 9.5.1.5.1](#). Abuse is always to be captured as an AE.

During the study, the investigator should be aware of the possibility of abuse or diversion of study drugs and should report any concern about mishandling, abuse, loss, theft, or diversion of study drugs by completing the Potential Abuse-related Medication Handling Event eCRF.

9.5.7 Confirmation of Medical Care by Another Physician

The investigator will instruct subjects to inform site personnel when they are planning to receive medical care by another physician. At each visit, the investigator will ask the subject whether he or she has received medical care by another physician since the last visit or is planning to do so in the future. When the subject is going to receive medical care by another physician, the investigator, with the consent of the subject, will inform the other physician that the subject is participating in the clinical study.

9.6 Data Quality Assurance

This study will be organized, performed, and reported in compliance with the protocol, standard operating procedures, working practice documents, and applicable regulations and guidelines. Site audits will be made periodically by the sponsor's or the CRO's qualified compliance auditing team, which is an independent function from the study team responsible for conduct of the study.

9.6.1 Data Collection

Data required by the protocol will be collected on the eCRFs and entered into a validated data management system that is compliant with all regulatory requirements. As defined by ICH guidelines, the CRF is a printed, optical, or electronic document designed to record all of the protocol-required information to be reported to the sponsor on each study subject.

Data collection on the eCRF must follow the instructions described in the CRF Completion Guidelines. The investigator has ultimate responsibility for the collection and reporting of all clinical data entered on the eCRF. The investigator or designee as identified on Form FDA 1572 (where applicable) must sign the completed eCRF to attest to its accuracy, authenticity, and completeness.

Completed, original eCRFs are the sole property of Eisai and should not be made available in any form to third parties without written permission from Eisai, except for authorized representatives of Eisai or appropriate regulatory authorities.

9.6.2 Clinical Data Management

All software applications used in the collection of data will be properly validated following standard computer system validation that is compliant with all regulatory requirements. All data, both eCRF and external data (eg, laboratory data), will be entered into a clinical system.

Electronic source (eSource) methodology may be used for some of the clinical efficacy assessments performed in this study.

9.7 Statistical Methods

All statistical analyses will be performed by the sponsor or designee. Statistical analyses will be performed using SAS software or other validated statistical software as required.

All statistical tests will be based on the 5% (2-sided) level of significance, except for the Bayesian methods on the primary endpoint.

9.7.1 Statistical and Analytical Plans

The statistical analyses of study data are described in this section. Further details of the analytical plan will be provided in the statistical analysis plan, which will be finalized before the first interim efficacy analysis.

9.7.1.1 Study Endpoints

See [Section 9.2.3](#) for a discussion of the rationale for the selection and clinical relevance of the primary study endpoint. Further information on the derived ADCOMS is described in [Section 9.5.1.3.1](#).

9.7.1.1.1 PRIMARY ENDPOINT

- Change from baseline in the derived ADCOMS at 18 months of treatment in MCI/Prodromal subjects

9.7.1.1.2 SECONDARY ENDPOINTS

Change from baseline in: (revised per Amendment 02)

- Total hippocampal atrophy at 12 and 18 months of treatment in MCI/Prodromal subjects as measured by vMRI
- The derived ADCOMS at 18 months of treatment in mild to moderate AD subjects (revised per Amendment 01)

9.7.1.1.3 EXPLORATORY ENDPOINTS

(revised per Amendments 01 and 02)

Change from baseline in:

- The derived ADCOMS at 12 months of treatment in MCI/Prodromal and mild to moderate AD subjects
- Total hippocampal volume at 12 and 18 months of treatment in mild to moderate AD subjects as measured by vMRI
- CSF A β (1-x) and A β (1-42) after 4 weeks and 18 months of treatment in MCI/Prodromal and mild to moderate AD subjects
- The following clinical assessments at 12 weeks and at 6, 9, 12, 15, 18, 19, and 21 months: ADAS-cog, CDR, MMSE, ISLT, CBB, and FAQ in MCI/Prodromal and mild to moderate AD subjects
- CSF biomarkers of neurodegeneration (eg, tau and p-tau) at 18 months of treatment in MCI/Prodromal and mild moderate AD subjects
- Plasma and CSF amyloid, and CSF BACE1 measurements after 4 weeks and 18 months of treatment, and during posttreatment follow-up in MCI/Prodromal and mild moderate AD subjects
- Left and right hippocampal, whole brain, and total ventricular volume at 6, 12, and 18 months in MCI/Prodromal and mild to moderate AD subjects as measured by vMRI
- Brain amyloid levels as measured by amyloid PET at 18 months in MCI/Prodromal and mild to moderate AD subjects
- The population PK parameters of E2609 including the effect of intrinsic and extrinsic factors (including *NAT2* phenotype) in MCI/Prodromal and mild to moderate AD subjects

9.7.1.2 Definitions of Analysis Sets

- The Randomized Set is the group of subjects who are randomized to study drug.
- The Safety Analysis Set is the group of subjects who receive at least 1 dose of study drug and have at least 1 postdose safety assessment.
- The Full Analysis Set (FAS) is the group of randomized subjects who receive at least 1 dose of study drug and have baseline and at least 1 postdose primary efficacy measurement.
- The Per Protocol (PP) Analysis Set is the subset of subjects in the FAS who sufficiently comply with the protocol. The PP Analysis Set will be used to conduct a sensitivity analysis of the primary efficacy endpoint. Details of the evaluability criteria will be determined before database lock and treatment unblinding, and will be specified in the statistical analysis plan.

- The PK Analysis Set is the group of subjects with at least 1 quantifiable E2609 plasma concentration accompanied by a documented dosing history.
- The PD Analysis Set is the group of subjects who have a baseline PD measurement and at least 1 posttreatment PD measurement.

9.7.1.3 Subject Disposition

The number of subjects screened, the number (percent) of subjects who failed screening, and the reasons for screen failure will be summarized, based on data reported on the Screening Disposition eCRF. The distribution of the number of randomized subjects enrolled by each site will be summarized for each randomized treatment group. The primary reasons for screen failures (did not meet inclusion or met exclusion criteria, AE, lost to follow-up, withdrawal of consent, and other) will be presented.

Study Completion: The number (percent) of randomized and treated subjects who completed the study and who withdrew from the study will be summarized according to the primary reason for discontinuation and secondary reason(s) for discontinuation, based on data reported on the Subject Disposition (Study Phase) CRF. The number (percent) will be presented by treatment group and total for subjects; randomized, not treated, treated, who completed the study, and withdrew from the study. The primary reasons for discontinuation from the study are: AE, lost to follow-up, subject choice, withdrawal of consent, pregnancy, study terminated by sponsor, and other. The secondary reasons for discontinuation from the study are: AE, subject choice, and other.

Completion of Study Treatment: The number (percent) of randomized and treated subjects who completed study drug and who discontinued from study drug will be summarized according to the primary reason for discontinuation and also according to secondary reason(s) for discontinuation, based on data reported on both the Subject Disposition (Study Phase) eCRF and ED from Study Drug eCRF. The number (percent) will be presented by treatment group and total for subjects; randomized, not treated, treated, who completed study drug, and discontinued from study drug. The primary reasons for discontinuation from the study drug are: AE, lost to follow-up, subject choice, withdrawal of consent, pregnancy, study terminated by sponsor, inadequate therapeutic response, and other. The secondary reasons for discontinuation from the study are: AE, subject choice, and other.

9.7.1.4 Demographic and Other Baseline Characteristics

Demographic and other baseline characteristics for the Safety Analysis Set and FAS will be summarized for each treatment group using descriptive statistics. Continuous demographic and baseline variables include age, MMSE and FAQ; categorical variables include sex, age group (≤ 65 years, age > 65 years), race, ethnicity, *ApoE4* status (positive or negative), prior treatment with AChEIs or memantine (no or yes), and clinical population (MCI/Prodromal AD or mild to moderate AD). (revised per Amendment 01)

9.7.1.5 Prior and Concomitant Therapy

All investigator terms for medications recorded in the eCRF will be coded to an 11-digit code using the World Health Organization Drug Dictionary (WHO DD) (Mar 2014). The number (percentage) of subjects who took prior and concomitant medications will be summarized on the Safety Analysis Set by treatment group, Anatomical Therapeutic Chemical class, and WHO DD preferred term. Prior medications will be defined as medications that stopped before the first dose of study drug. Concomitant medications will be defined as medications that (1) started before the first dose of study drug and were continuing at the time of the first dose of study drug, or (2) started on or after the date of the first dose of study drug up to the date of the last dose. All medications will be presented in subject data listings.

Medications taken within the 12-week Follow-Up period will also be recorded.

9.7.1.6 Efficacy Analyses

The MCI/Prodromal Cohort

The study in the MCI/Prodromal cohort is based on Bayesian adaptive design. Frequent interim analyses will be performed to assess the probability of early success and futility and to make early stopping decisions. Response adaptive randomization will be used to update the randomization probability among treatment groups at each interim analysis. Key definitions relevant to the Bayesian aspects of the adaptive design are given below.

Study Definitions

- **Maximum Effective Dose (d_{Max}):** The dose that achieves the greatest treatment effect.
- **ED₉₀:** The lowest dose that achieves at least 90% of the d_{Max} treatment effect in the derived ADCOMS.
- **Early Success:** The study in the MCI/Prodromal cohort will meet early success criteria if the probability that the ED₉₀ at 18 months of treatment achieves 25% improvement over placebo is at least 80%. Early success is achieved before all MCI/Prodromal subjects complete 18 months of treatment and can only be determined after at least 200 MCI/Prodromal subjects have been randomized. If early success is declared before full randomization, the randomization of new MCI/Prodromal subjects will stop but subjects already randomized into the study will receive the full 18 months of treatment (following confirmation from the Sponsor's Senior Management).
- **Futility:** The study in the MCI/Prodromal cohort will meet statistical futility criteria if the probability that the ED₉₀ is better than placebo by the clinically significant difference of 25% is less than 5% at 18 months of treatment. The statistical futility boundary is binding; if the statistical futility boundary is crossed the study will be considered to have failed.

- **Study Success:** The study in the MCI/Prodromal cohort will be considered a success if an ED_{90} at 18 months treatment has at least an 80% probability of achieving 25% improvement over placebo at either an interim analysis or at the final analysis.

The Mild to Moderate AD Cohort (revised per Amendment 01)

All mild to moderate AD subjects will be included in the efficacy evaluations of the Mild to Moderate AD cohort. The analysis of the Mild to Moderate AD cohort is based on the group sequential design. Interim analyses in the Mild to Moderate AD cohort will only be performed after the MCI/Prodromal cohort crosses the early success boundary. The early efficacy signal based on the change from baseline of ADCOMS at 18 months is defined as crossing the interim-analysis boundaries for overwhelming efficacy in the mild to moderate AD population. The O'Brien-Fleming (OF) boundaries based on Lan-DeMets alpha spending function will be used to assess overwhelming efficacy. The corresponding OF boundaries based on P values will be 0.076, 0.0221, and 0.0423 for the first, second, and final analyses, respectively, according to 2 planned interim analyses at the 60% and 80% information fraction. (revised per Amendment 01)

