The null and alternative hypotheses and the statistical test are the same as those for vMRI. To estimate the sample size for the amyloid PET imaging subgroup at 18 months, a common SD of the change from baseline was estimated at 0.33 and a reasonable mean difference between treatment and placebo was estimated as 0.25 (standardized uptake value ratio [SUVR]). Assuming a moderate dose-response, the best dose would achieve a difference of 0.25 (SUVR) and the middle and low doses would achieve a difference of 0.2 and 0.15 (SUVR), respectively; this would require a total of 100 subjects from all 4 arms at 18 months to achieve 80% power.

9.7.2.2 Sample Size Rationale for the Mild to Moderate AD Cohort (revised per Amendment 01)

ADCOMS at Month 18

The null hypothesis is that there is no difference between active dose and placebo. There are 2 null hypotheses corresponding to 2 active doses. The alternative hypothesis is that at least 1 null hypothesis is false. The null hypotheses will be tested using Dunnett's test with 2-sided alpha of 0.05 as described for the Mild to Moderate AD cohort in [Section 9.7.1.6.2](#). The statistical power was estimated through simulation for the dose-response assumption that the percent reduction in change from baseline of ADCOMS at 18 months compared with placebo would be 33% and 50% corresponding to the 2 doses, respectively. The estimated power for the actual planned 200 mild to moderate AD subjects is approximately 80% assuming a 2-sided alpha of 0.05. (revised per Amendment 01)

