A group sequential design will be used for the Mild to Moderate AD cohort. (revised per Amendment 01) This design includes 3 looks, 2 interim looks (when 60% and 80% information fractions are achieved) and 1 final look. The information fraction is the number of assessments in all treatment arms divided by the total number of expected assessments. Interim analyses will be performed after the MCI/Prodromal cohort crosses the early success boundary. The corresponding efficacy boundaries will be 0.076, 0.022, and 0.0423 for the first, second, and final analyses, respectively. If the actual information fraction during the interim analyses is different from 60% or 80% at the interim, the efficacy boundaries will be adjusted based on the actual information fraction.

If early success in the MCI/Prodromal cohort is not achieved before the final analysis that is performed when all subjects have completed 18 months treatment, then only a final analysis will be performed in mild to moderate AD subjects. In the event of futility in the MCI/Prodromal cohort, an analysis will be performed for the Mild to Moderate AD cohort based on the data for mild to moderate AD subjects available at that time. (revised per Amendment 01)

Randomization into the Mild to Moderate AD cohort will remain at a fixed schedule throughout Stage B. (revised per Amendment 01)

The interim analyses in the Mild to Moderate AD cohort will be conducted by an independent analysis group. (revised per Amendment 01)

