- **Study Success:** The study in the MCI/Prodromal cohort will be considered a success if an ED₉₀ at 18 months treatment has at least an 80% probability of achieving 25% improvement over placebo at either an interim analysis or at the final analysis.

The Mild to Moderate AD Cohort (revised per Amendment 01): All mild to moderate AD subjects will be included in the efficacy evaluations of the Mild to Moderate AD cohort. The analysis of the Mild to Moderate AD cohort is based on the group sequential design. Interim analyses in the Mild to Moderate AD cohort will only be performed after the MCI/Prodromal cohort crosses the early success boundary. The early efficacy signal based on the change from baseline of ADCOMS at 18 months is defined as crossing the interim-analysis boundaries for overwhelming efficacy in the mild to moderate AD population. The O'Brien-Fleming (OF) boundaries based on Lan-DeMets alpha spending function will be used to assess overwhelming efficacy. The corresponding OF boundaries based on *P* values will be 0.076, 0.0221, and 0.0423 for the first, second, and final analyses, respectively, according to 2 planned interim analyses at the 60% and 80% information fraction. (revised per Amendment 01)

Analysis for the primary endpoint

Primary analysis of primary endpoint

The primary analysis will be based on MCI/Prodromal subjects from the FAS with the prespecified censoring rule applied. The primary endpoint is the change from baseline to 18 months in the derived ADCOMS. The dose-response of the primary endpoint is modelled with a first-order normal dynamic linear model, where Normal and Inverse-Gamma priors are used. The primary efficacy analysis will calculate the Bayesian posterior probability that the dose identified is the most likely ED₉₀ dose that achieves 25% improvement over the placebo arm. At each interim analysis and the final analysis, 2 Bayesian probabilities will be summarized for each active dose: the probability it is the ED₉₀ dose and the probability of achieving 25% improvement over the placebo arm.

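### The first-look O'Brien-Fleming boundary for the mild to moderate AD cohort is printed as 0.076 where the stated design gives 0.0076; applied as written, type I error is 9.7%, not 5%

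*Protocol*

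**What the plan says.** Section 9.7.1.6 names the method for the mild to moderate AD cohort: "The O'Brien-Fleming (OF) boundaries based on Lan-DeMets alpha spending function will be used to assess overwhelming efficacy". Section 9.7.3 sets the timing: "This design includes 3 looks, 2 interim looks (when 60% and 80% information fractions are achieved) and 1 final look". The overall level is 5% two-sided, both in general (section 9.7: "All statistical tests will be based on the 5% (2-sided) level of significance, except for the Bayesian methods on the primary endpoint") and for this cohort's comparison of two doses with placebo (section 9.7.2.2: "The null hypotheses will be tested using Dunnett's test with 2-sided alpha of 0.05").

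The boundaries are then given as numbers. Section 9.7.1.6: "The corresponding OF boundaries based on P values will be 0.076, 0.0221, and 0.0423 for the first, second, and final analyses, respectively". Section 9.7.3: "The corresponding efficacy boundaries will be 0.076, 0.022, and 0.0423 for the first, second, and final analyses, respectively". The synopsis repeats them under Efficacy Analyses ("values will be 0.076, 0.0221, and 0.0423 for the first, second, and final analyses, respectively") and under Interim Analyses. The first value is 0.076 every time.

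Two further rules bear on how the numbers are used. The interims are conditional: "Interim analyses in the Mild to Moderate AD cohort will only be performed after the MCI/Prodromal cohort crosses the early success boundary". Section 9.7.3 also says that the boundaries are adjusted if the actual information fraction is not 60% or 80%.

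**The concern.** O'Brien-Fleming spending is meant to make the first look hard to pass. Here the first threshold, 0.076, is looser than the second (0.0221) and the third (0.0423). It is also larger than the total alpha of 0.05, so no spending function with that total could produce it.

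The number is a decision rule. Section 9.7.1.6 defines the cohort's early efficacy signal as crossing these boundaries for overwhelming efficacy. As printed, a first-look p-value of 0.07 would qualify, although it would fail an ordinary single-look test at 5%. The endpoint, ADCOMS at 18 months in this cohort, is a listed secondary endpoint (section 9.7.1.1.2), and the Introduction (section 7) says the study's results will guide the decision to enter Phase 3.

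**Working it through.** **Inputs**
- Two-sided alpha 0.05: sections 9.7 and 9.7.2.2.
- Lan-DeMets spending of O'Brien-Fleming type: section 9.7.1.6.
- Information fractions t = 0.6, 0.8, 1.0: sections 9.7.1.6 and 9.7.3.
- Printed nominal p-values 0.076, 0.0221 (0.022 in section 9.7.3) and 0.0423.

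**Step 1: alpha spent.** With 0.025 on each side, cumulative two-sided spending is

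α(t) = 4 × [1 − Φ(z / √t)], where z = Φ⁻¹(0.9875) = 2.2414.

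- t = 0.6: z/√t = 2.894, α = 0.00762
- t = 0.8: z/√t = 2.506, α = 0.02442
- t = 1.0: z/√t = 2.241, α = 0.05000

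**Step 2: boundaries.** At the first look the nominal p-value equals the alpha spent. The later boundaries were solved by recursive numerical integration, so that cumulative crossing probability under the null equals α(t).

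| Look | Information | z boundary | Nominal p, recomputed | Printed |
|---|---|---|---|---|
| 1 | 60% | 2.669 | 0.00762 | 0.076 |
| 2 | 80% | 2.289 | 0.02210 | 0.0221 |
| 3 | 100% | 2.031 | 0.04229 | 0.0423 |

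The second and third printed values are reproduced to four decimals, which identifies the design that was intended. The first is out by a factor of 10.

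**Step 3: other readings.** A single spending function on the full 0.05 gives 0.0114 / 0.0244 / 0.0392. The classic O'Brien-Fleming boundary gives 0.0085 / 0.0227 / 0.0416. Neither gives 0.076 at the first look, and neither fits the other two printed values as well.

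**Step 4: type I error.** Probability of first crossing at each look under the null, by the same recursion:

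| Boundary set | Look 1 | Look 2 | Look 3 | Total |
|---|---|---|---|---|
| 0.076 / 0.0221 / 0.0423 (printed) | 0.0760 | 0.0041 | 0.0166 | 0.0967 |
| 0.0076 / 0.0221 / 0.0423 | 0.0076 | 0.0168 | 0.0256 | 0.0500 |

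A simulation of 1,000,000 trials gives 0.0966 for the printed set. Using 0.022 at the second look leaves the total at 0.0967. If the boundaries are applied to a Dunnett-adjusted p-value for two doses, the totals are about 0.098 as printed and 0.051 with 0.0076.

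**The case against.** The arithmetic is not open to dispute; the case on the other side concerns how often the error would act.

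- **The interims are conditional.** Without early success in the MCI/Prodromal cohort, the AD cohort has only a final analysis and 0.076 is never used. If early success comes so late that only the 80% and final looks occur, the printed 0.0221 and 0.0423 give 0.0221 + 0.0263 = 0.048, with no inflation. This stands. But early success is the situation for which the boundaries were written, so the rule is wrong when it is needed.
- **The boundaries are recalculated if the fraction differs.** Information is counted in assessments, so exactly 60% may be unusual. Recalculation from the named spending function gives 0.0065 at 58% and 0.0088 at 62%, nowhere near 0.076. This stands as mitigation, but it leaves the printed number in force at the planned 60%. It also makes the rule incoherent: recalculation at 70% gives 0.0148, so a look with more information would face a threshold about five times stricter than the printed one at 60%.
- **The stakes are limited.** This is a secondary endpoint in a Phase 2 study, and the text shown attaches no stopping of AD enrolment or treatment to a crossing. The two correct later values also make the slip easy to see. All true, but a pre-specified threshold corrected informally after data have accrued would look post hoc, and an analysis plan using 0.0076 would contradict the protocol.
- **Only part of the document is shown.** The claim that nothing corrects the value covers the text supplied. That text includes the statistical sections in two versions of the protocol, and both carry 0.076.

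**Conclusion.** The concern holds. Under the protocol's own method, alpha and timing, the first boundary is 0.0076; the printed 0.076 is a tenfold error. The three-look rule as written has a two-sided type I error of 9.7% instead of 5.0%, and the first look alone takes 7.6%.

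The 9.7% assumes that the MCI/Prodromal cohort has reached early success, that both AD interims fall at exactly 60% and 80% information, and that the printed values are applied without recalculation. Outside those conditions the inflation shrinks or disappears. That limits how often the error matters but does not make the stated threshold right. It must be corrected. The difference between 0.0221 and 0.022 for the second look is rounding and has no material effect.

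**What to change.** Replace 0.076 with 0.0076 wherever the boundaries are stated: section 9.7.1.6, section 9.7.3, and the synopsis under both Efficacy Analyses and Interim Analyses. While editing, write the second value as 0.0221 throughout, for consistency only. With 0.0076 / 0.0221 / 0.0423 the overall error returns to 0.0500. Make the change in a protocol amendment before the first AD interim. It is a wording correction: sample size, timing of looks and conduct of the trial are unaffected.
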